17.6 A Tool to Assess Quality of Life (ATAQ)

For Part B of the study only, the ATAQ questionnaires (ATAQ Symptoms and ATAQ Impacts) will be self-administered at Baseline (Day 1), Day 8, Day 15, Day 28, Day 45, and Day 58 to assess subjects' disease symptoms across three domains (dyspnea, cough, and energy level), impact on quality of life across 4 domains (dyspnea, cough, energy level, and global impact), and a set of questions pertaining to oxygen use.

17.6.1 ATAQ Symptoms Domains

The ATAQ Symptoms questionnaire contains 3 domains (dyspnea, cough, and energy level). The dyspnea domain (Questions 1-12) assesses subjects' ability to perform physical activities in the previous 24 hours. Responses are measured using a Likert scale (0-4) as applicable to subjects who completed the activities assessed. Subjects who found the assessed activity for Questions 1, 2, 4-10, and 12 too difficult to perform due to their disease symptoms receive a score of 5 for the question, and subjects who did not complete the activity for other reasons receive no score. The cough domain (Questions 13-18) measures subjects' cough symptoms in the previous 24 hours, and the energy level domain (Questions 19-23) measures subjects' energy level in the previous 24 hours. Responses to questions within the cough and energy level symptoms domains measured on a Likert scale (0-4).

Questions 19, 20, and 21 require reverse mapping for scoring and will be mapped as follows:

- 0 mapped to 4
- 1 mapped to 3
- 2 mapped to 2
- 3 mapped to 1
- 4 mapped to 0

Each domain score ranges from 0 to 100%. Higher scores indicate worse health status in terms of subjects' symptoms. The Symptoms total score is an average of the domain scores. Details of the scoring algorithm are provided in the Appendix to the SAP.

17.6.2 ATAQ Impacts Domains

All questions within the Impact domains are assessed using a Likert scale (0-4). The impact of disease is assessed through subjects' recall of events during the previous week. Each domain (dyspnea, cough, energy level, and global impact) is scored on a scale of 0 to 100%, where 100% indicates worse health status in terms of the impact of disease on subjects' quality of life. The dyspnea domain is defined for Questions 1-6. The cough domain is defined for Questions 7-11. The energy domain is defined for Questions 13-14. The global impact domain is defined for Questions 12 and 15-21. The Impacts total score is an average of the ATAQ Impacts domain scores. The same reverse mapping as described in the previous section is required for Questions 3, 17, 18, 19, 20, and 21.

Scoring for both ATAQ questionnaires will be based only on observed data. No imputation for missing values will be used to calculate ATAQ scores.

17.6.3 Analysis of ATAQ Data

Summary statistics for each ATAQ domain will be displayed by study drug and all GBT440, and by visit for the Efficacy-Evaluable population. The change from baseline to each post-baseline visit also will be summarized.

ANCOVA models will be used to analyze the effect of treatment on the change from baseline with baseline value as a covariate. Least squares (LS) means and SEs will be displayed for the change from baseline in each treatment group and for all GBT440.

LS means (95% CI) and p-values from the models will be used to make the following comparisons:

- GBT440 600 mg – Placebo
- GBT440-900 mg – Placebo
- GBT440-1500 mg – Placebo
- All GBT 440 – Placebo

Responses to questions regarding supplemental oxygen use will be summarized with the number and percentage of subjects in each treatment group and for all GBT440 at each visit. Flow rates of oxygen during sleep, during physical activity, and during rest also be summarized with continuous descriptive statistics if at least 2 subjects in each treatment group are on supplemental oxygen. The change from baseline to each post-baseline visit in flow rates will be included as applicable.

17.7 Cardiopulmonary Exercise Testing (CPET)

Cardiopulmonary exercise testing (CPET) parameters are computed using data collected on the CRF from all treated subjects at Day 2 and Day 29. The following CPET parameters by stage include:

Stage	CPET Parameters
Rest	HR, Extime, VCO ₂ , VO ₂ , RER, SpO ₂ , Art_O ₂ , Art_O ₂ Sat, Art_CO ₂ , Lactate
VentThrsh	HR, Extime, VCO ₂ , RER, SpO ₂ , Art_O ₂ , Art_O ₂ Sat, Art_CO ₂ , Lactate, VENT/VO ₂
LactThrsh	HR, Extime, VCO ₂ , VO ₂ , RER, SpO ₂ , Art_O ₂ , Art_O ₂ Sat, Art_CO ₂ , Lactate, Watts
Max	HR, Extime, VCO ₂ , VO ₂ , RER, SpO ₂ , Art_O ₂ , Art_O ₂ Sat, Art_CO ₂ , Lactate, Watts

- HR = Heart Rate (bpm)
- Extime = Exercise time (elapsed time from start to end of stage)
- VCO₂ = Carbon Dioxide Excretion (mls/min)
- VO₂ = Oxygen Consumption (ml/min)
- RER = Respiratory Exchange Ratio (VCO₂/VO₂)
- SpO₂ = Oxygen Saturation (%)
- Art_O₂ = Arterial Oxygen (mmHg)
- Art_O₂Sat = Arterial Oxygen Saturation (%)
- Art_CO₂ = Arterial Carbon Dioxide (mmHg)
- Lactate = Lactate Concentration (mmol/L)
- Watts = Exercise Output (Watts)
- VentThrsh = Ventilatory Threshold
- LactThrsh = Lactic Acid Threshold

Summary statistics for the CPET parameters at the following endpoints will be displayed by study drug and for all GBT440 by visit using the Efficacy-Evaluable population. Summary statistics for the change from Day 2 to Day 29 will be included in the summary.

Parameter	Endpoint
Exercise Time (Minutes)	Max – Rest
Watts	Max
VO ₂ (ml/min/kg)	Max
SpO ₂ (%)	Max – Rest
Arterial Oxygen (mmHg)	Max – Rest
Arterial Oxygen Saturation (%)	Max – Rest
Lactate (mmol/L)	Max – Rest
VO ₂ (ml/min/kg)	VentThrsh / Max
Watts	VentThrsh / Max
Heart Rate (bpm)	Rest
Heart Rate (bpm)	Max – Rest
RER	Max
Arterial Carbon Dioxide (mmHg)	Max – Rest
Heart Rate (bpm)	VentThrsh – Rest
Exercise Time (Minutes)	VentThrsh – Rest
VENT/VO ₂ (ml/min/kg)	VentThrsh
SpO ₂ (%)	VentThrsh – Rest
Arterial Oxygen (mmHg)	VentThrsh – Rest
Arterial Carbon Dioxide (mmHg)	VentThrsh – Rest
Arterial Oxygen Saturation (%)	VentThrsh – Rest

VO₂ (ml/min) will be divided by the subject’s last non-missing body weight measurement before each analysis timepoint (ie Day 2 or Day 29) to obtain VO₂ (ml/min/kg).

ANCOVA models will be used to analyze the effect of treatment on the change from Day 2 with the Day-2 value as a covariate. Least squares (LS) means and SEs will be displayed for the change from Day 2 in each treatment group and for all GBT440.

LS means (95% CI) and p-values from the models will be used to make the following comparisons:

- GBT440 600 mg – Placebo
- GBT440-900 mg – Placebo
- GBT440-1500 mg – Placebo
- All GBT 440 – Placebo

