1.3. Rationale for Study

GBT440, a hemoglobin modifier that causes a left-shift in the oxy-hemoglobin dissociation curve (ODC) has the potential to enable increased oxygen uptake in the lungs and O₂ saturation, resulting in improved oxygen delivery to tissues. A key therapeutic goal for IPF patients with GBT440 is to reduce hypoxemia and improve the associated debilitating symptoms and functional impairment. Supplemental oxygen therapy is a well-established treatment in IPF and other chronic hypoxemic pulmonary diseases where it improves symptoms, functional status and (in the case of Chronic Obstructive Pulmonary Disease) improves survival. Supplemental oxygen therapy has disadvantages, however, which can negatively impact patient quality of life including the burden and decreased mobility from the required oxygen delivery devices, local complications, poor compliance and inadequate symptomatic relief. GBT440 therapy may be able to provide many of the same clinical benefits of oxygen therapy without the negative aspects of oxygen supplementation. GBT440 could also be useful as an adjunct to oxygen therapy in more severe subjects who are not adequately oxygenated despite noninvasive oxygen therapy or to allow the use of lower flow, more convenient oxygen equipment for the same clinical benefit. This study will gather preliminary data, across a range of GBT440 doses, to determine whether GBT440 could improve: oxygen saturation at rest and with exercise, IPF-related symptoms and exercise capacity.

GBT440 has been administered to healthy subjects and subjects with SCD. Overall, multiple doses of GBT440 have been well tolerated across a broad range of doses (300 mg–1000mg) for up to 90 days. Results from this study will inform future development of GBT440 in IPF subjects.

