1.5.4. Potential Risk of GBT440 Treatment

1.5.4.1. Tissue Hypoxia

There is a theoretical risk of tissue hypoxia in subjects treated with GBT440 based on the mechanism of action and potential associated impairment in O₂ offloading at the tissues. However, in vitro data show that GBT440 modified Hb- remains sensitive to the Bohr effect and in vivo data from animal models of pulmonary hypoxemia are consistent with increased oxygen extraction and consumption by tissues. Furthermore, clinical data from subjects receiving study drug and those participating in maximal cardio-pulmonary exercise tests in the ongoing Phase I/II study, GBT440-001, have not identified a concern with tissue hypoxia. Please refer to the GBT440 IB for further details.

IPF subjects in this study will be closely monitored for subclinical evidence of worsening tissue hypoxia as measured by erythrocytosis, increased resting heart rate and erythropoietin and laboratory tests indicating organ injury (e.g. liver aminotransferases). To date, none of these findings have been documented in Part A subjects dosed in this study.

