5.5.4. Cardiopulmonary Exercise Testing (CPET)

Symptom-limited cardiopulmonary exercise testing using a bicycle ergometer will be performed on Day 2 and Day 29. At baseline and during the exercise period the collected data will include but is not limited to: SpO₂ and arterial blood gases, VO₂ max, ventilation and lactate thresholds. Guidelines developed by ATS and American College of Chest Physicians will be used for conducting the test and interpreting the results ([ATS 2003](#)).

Instructions for the conduct of the CPET will be provided in a separate manual. An arterial line placement will be part of the CPET procedure. If the subject refuses arterial line placement they may still undergo the CPET assessments without the arterial line.

Agreement to undergo the CPET is not required for entry into the study; but participation is strongly encouraged.

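### CPET saturation is analysed only as a difference from rest, so any rise common to rest and exercise drops out and the trial's only arterial saturation is never reported as a level

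*SAP*

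**What the plan says.** SAP 17.7 first lists what is recorded at four CPET stages: rest, ventilatory threshold, lactate threshold and maximum. SpO2, arterial oxygen and arterial oxygen saturation are recorded at all four. A second table then fixes what is analysed: "Summary statistics for the CPET parameters at the following endpoints will be displayed by study drug and for all GBT440". Change from Day 2 to Day 29 on those endpoints goes into an ANCOVA with the Day 2 value as covariate, with each dose and all GBT440 compared with placebo.

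The arterial saturation rows read "Arterial Oxygen Saturation (%) Max – Rest" and "Arterial Oxygen Saturation (%) VentThrsh – Rest". SpO2 and arterial oxygen appear in the same two forms. Heart rate is the only parameter with a row for its resting value.

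The lactate-threshold stage is defined ("LactThrsh = Lactic Acid Threshold") with 11 parameters, including VO2 and Watts, and Protocol 5.5.4 names "ventilation and lactate thresholds" among the data to collect. No endpoint row uses that stage.

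Protocol 1.3 says the study gathers preliminary data on whether GBT440 could improve "oxygen saturation at rest and with exercise, IPF-related symptoms and exercise capacity".

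**The concern.** GBT440 is expected to raise saturation by shifting the oxygen dissociation curve to the left, at rest as well as during exercise. A maximum-minus-rest endpoint shows only how much more the drug does at maximum than at rest. If it raised saturation equally at both, the planned CPET tables would show no effect on saturation. If it raised resting saturation more, they would show a worsening.

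The SAP treats the walk test differently. SAP 3.2 and 16 analyse absolute resting, end-of-walk and lowest SpO2 as secondary endpoints, and SAP 17.1 adds the differences from rest as further exploratory endpoints. For CPET only the differences are planned, and no reason is given. The walk test uses pulse oximetry, so it cannot stand in for arterial saturation.

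**Working it through.** The plan states no power or effect size for CPET, so there is no figure to reproduce. The check is a count, an identity and an illustration.

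**1. Count of the SAP 17.7 endpoint table**

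| Type of row | Rows |
|---|---|
| All endpoints | 20 |
| Oxygenation (SpO2, arterial oxygen, arterial saturation; maximum and ventilatory threshold) | 6 |
| – of these, minus rest | 6 |
| – of these, saturation in % | 4 |
| Using the lactate threshold | 0 |
| No subtraction of rest | 7 |

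The seven are Watts at maximum, VO2 at maximum, VO2 and Watts as ventilatory threshold / maximum, resting heart rate, RER at maximum, and VENT/VO2 at ventilatory threshold. None is an oxygenation measure.

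**2. Identity (no assumption needed)**

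Change in (Max – Rest) = change at Max – change at Rest. With illustrative changes in saturation points:

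| Change at rest | Change at maximum | Planned endpoint | Absolute maximum |
|---|---|---|---|
| +2 | +2 | 0 | +2 |
| +3 | +3 | 0 | +3 |
| +1 | +4 | +3 | +4 |
| +2 | +4 | +2 | +4 |
| +3 | +2 | –1 | +2 |

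**3. How much a left shift would lose (all inputs assumed)**

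Saturation = 100 / (1 + (P50/PO2)^2.7), with P50 moved from 27 mmHg to 25, 24, 22, 20 or 18, and rest/maximum PO2 of 70/50, 60/45, 60/40 or 80/55 mmHg. PO2 is held fixed while P50 moves. That gives 20 scenarios.

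Worked example, P50 27 to 20, PO2 60 at rest and 45 at maximum:

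- Rest: 89.6 to 95.1, gain 5.5.
- Maximum: 79.9 to 89.9, gain 10.0.
- Max – Rest: 10.04 – 5.48 = 4.56, reported as +4.6.
- Share of the gain at maximum that is kept: 4.56 / 10.04 = 45%.

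Over the 20 scenarios the share kept runs from 43% to 59%. The endpoint is positive in every one, from +1.2 to +8.7 points.

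The model compares undosed with dosed blood. The planned contrast is change from Day 2, which follows the first dose, so these sizes do not predict the trial's result.

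**The case against.** A difference from rest is a legitimate measure. It describes exercise desaturation, which the eligibility criteria select for (resting SpO2 of at least 88%, then a fall below 88% with at least a 5% absolute decrease on walking) and which the dose rationale in Protocol 1.5.3 names. A left shift raises saturation more where PO2 is lower, so the endpoint should still move in the right direction, as it does in all 20 scenarios. This stands: the effect is attenuated, not hidden, unless the rise is equal at both stages. It is a reason to keep the difference rows.

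Absolute SpO2 at rest and on exercise is already analysed against placebo in the 6MWT. This also stands, and it confines the real gap mainly to arterial saturation. The two arterial oxygen rows are in mmHg and are outside the point: a left shift raises saturation at a given PO2, so subtracting resting PO2 does not remove the saturation gain.

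The stakes are modest. CPET is exploratory, is not required for entry, and may be done without an arterial line (Protocol 5.5.4). SAP 10.3 lists all data by subject and SAP 1 allows supplementary analyses, so no data are lost. The remaining gap is in what is specified in advance, which matters more because the sponsor is unblinded in Part B.

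A reader might infer that CPET cannot answer the questions it was included for. The documents do not support this. The stated objective is only the effect on CPET parameters, and exercise-specific gains, VO2 Max, Watts Max, ventilatory-threshold measures and "Lactate (mmol/L) Max – Rest" are all analysed. Nor does the unused lactate threshold leave tissue hypoxia unmonitored. The exercise tests said in Protocol 1.5.4.1 to "have not identified a concern with tissue hypoxia" belong to GBT440-001. For this trial the same section names other markers, including resting heart rate, which has its own CPET row.

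**Conclusion.** The point holds as a gap in an exploratory analysis that is cheap to close. All four CPET saturation endpoints remove whatever gain rest and exercise share, and the level of arterial saturation, measured only in CPET, is never tabulated or compared with placebo. That an equal gain scores zero is arithmetic. That roughly half of the gain at maximum survives (43 to 59%) depends on the assumed curve and PO2 values and illustrates the order of the loss only. The unused lactate-threshold stage is a secondary, minor omission, and SAP 19 does not list it as a change from the protocol.

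**What to change.** In the SAP 17.7 endpoint table, add SpO2 and arterial oxygen saturation at rest and at maximum, each as its own row with the same summaries and ANCOVA. Keep the difference rows and describe them as measures of exercise desaturation.

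For the lactate threshold, either add VO2 and Watts at that stage or state that the stage is listed only.

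Cost: no new procedure, visit or CRF field. The table now yields 20 × 4 = 80 unadjusted comparisons. The four saturation rows add 4 × 4 = 16, and the two lactate-threshold rows, if taken, add 2 × 4 = 8. No multiplicity scheme is disturbed, since SAP 10.4 has none. The arterial rows may be sparse because both CPET and the arterial line are optional, so show the number of subjects beside each estimate.

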17.8 Spirometry and DLco

Spirometry and DLco are assessed at Screening (Baseline), Day 28, and Day 58. Spirometry and DLco parameters include forced expiratory volume in 1 second (FEV1) actual (L) and predicted (%), FVC actual (L) and predicted (%), FEV1/FVC (actual and predicted), DLco actual (ml/mmHg/min), and DLco adjusted (%).

Summary statistics for the spirometry and DLco parameters will be displayed by study drug and all GBT440, and by visit for the Efficacy-Evaluable population. The change and percent change from baseline to each post-baseline visit also will be summarized.

Analysis of covariance models (ANCOVA) will be used to analyze the effect of treatment on the change from baseline and the percent change from baseline for each parameter with the baseline value as a covariate. Least squares (LS) means and SEs will be displayed for the change and percent change from baseline in each treatment group and for all GBT440.

LS means (95% CI) and p-values from the models will be used to make the following comparisons:

- GBT440 600 mg – Placebo
- GBT440-900 mg – Placebo
- GBT440-1500 mg – Placebo
- All GBT 440 – Placebo

17.9 End of Study Questionnaire

The End of Study Questionnaire is an 8-item survey to evaluate the subjects' experience while on the study including symptoms, changes in oxygen saturation and use. The questionnaire is a self-administered survey to be completed during the Day-58 visit. The survey is to be completed by subjects enrolled under Part B of the trial. All responses will be summarized with the number and percentage of subjects in the Safety population by study drug and all GBT440.

18. Interim Analyses

In Part A of the study, two unblinded interim analyses of the primary and secondary endpoints are planned: i) when approximately 9 subjects have completed their Day-28 study visit and ii) when approximately 18 subjects have completed their Day-15 study visit.

19. Changes from Protocol-Stated Analyses

Protocol	SAP Change	Rationale
Exploratory endpoint: Time to first SpO2 < 88% that is sustained for at least 10 seconds during the 6MWT at days 15 and 28.	Exploratory endpoint: Time to first SpO2 < 88% during the 6MWT at days 15 and 28.	Did not collect SpO2 in seconds on CRF therefore cannot confirm “at least 10 seconds” as per the protocol definition.
	Inclusion of additional exploratory endpoints: change from end of 6MWT to rest and change from lowest SpO2 to rest	Not specified in protocol.
Efficacy-Evaluable Population: All randomized subjects who received at least 15 days of study drug treatment will be included in the Efficacy-Evaluable population.	Efficacy-Evaluable Population: All randomized subjects who received at least 14 days of study drug treatment will be included in the Efficacy-Evaluable population.	Half of 28 days (complete dosing) is 14.

20. References

Not Applicable.

21. Appendices

Saint George’s Respiratory Questionnaire Manual

ATAQ Scoring Algorithm

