3.4 Statistical Hypotheses

This phase 2 study is designed to evaluate the safety and tolerability of multiple doses of GBT440 administered to subjects with IPF. No formal hypotheses are specified for this study.

4. General Study Design

This study is a randomized, placebo-controlled trial that will be conducted in two parts. Together, Parts A and B will provide safety and efficacy data across a range of GBT440 doses that are expected to improve oxygen saturation in the enrolled subjects.

- In Part A (Figure 1), eligible IPF subjects will be randomized 1:1:1 to receive GBT440 900 mg (n = 6) or 600 mg (n = 6), or placebo (n = 6) administered orally as 300 mg capsules once daily for 28 days. The study site, subjects, CRO statistician and Sponsor will be blinded to study treatment.
- In Part B (Figure 2), eligible IPF subjects will be randomized 3:1:1 to receive GBT440 1500 mg (n = 9) or 600 mg (n = 3), or placebo (n = 3) administered orally as 300 mg capsules once daily for 28 days in which the study site and subjects are blinded to study treatment. The Sponsor and CRO statistician will be unblinded to study treatment.

Subjects on a stable dose of pirfenidone or nintedanib and/or N-acetyl cysteine are eligible for entry into the study.

After the Screening visit, the study includes the following study periods:

- Treatment period (28 days): subjects will be randomized (1:1:1) to one of three treatment groups in Part A and randomized (3:1:1) to one of three treatment groups in Part B; subjects will receive:

Part A:

- Group 1: GBT440 900 mg; three 300 mg GBT440 capsules, daily orally.
- Group 2: GBT440 600 mg; two 300 mg GBT440 capsules and one placebo capsule, daily orally.
- Group 3: Placebo: three placebo capsules, daily orally.

Part B:

- Group 1: GBT440 1500 mg; five, 300 mg GBT440 capsules, daily orally.
 - Group 2: GBT440 600 mg; two 300 mg GBT440 capsules and three placebo capsule, daily orally.
 - Group 3: Placebo: five placebo capsules, daily orally.
- Safety follow-up (30 days): safety will be assessed for at least 5 half-lives after the last dose of GBT440.

Figure 1 Study Design – Part A

[figure not shown]
[figure not shown]

Figure 2 Study Design – Part B

Subjects who do not complete at least 10 days of dosing for reasons unrelated to toxicity may be replaced.

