- ^m PK blood samples during the treatment period should be collected on Days 1 and 28: pre-dose, and 2 hours post dose (+/- 15 minutes); Day 2: 24 hours (+/- 2 hours) after the Day-1 dose *and* prior to receiving the Day-2 dose; Days 8 & 15: pre-dose only. Also see Protocol Section 5.6.
- ⁿ Instructions for per-protocol performance of the 6-minute walk (and Borg dyspnea scale) and cardio-pulmonary exercise tests are provided in the procedure manual. Note: The baseline 6MWT performed during screening must be performed within 7 days of the Day-1 visit.
- ^o An unblinded study pharmacist will prepare daily doses of study drug, dispensed into 30 mL high-density polyethylene (HDPE) bottles. Each bottle (or dose) is packaged individually with 3 capsules of active or placebo or both specific to each subject’s assigned treatment group. Subjects who have their dose modified during the study must return to the site to have the modified dose of study drug dispensed by the unblinded pharmacist.
- ^p Subjects should not administer study drug on the morning of these study visits. Study drug will be administered by the study staff after completion of all pre-dose assessments.
- ^q The SGRQ, ATAQ, and UCSD questionnaires and cough VAS should be self-administered by the subject, using the paper forms provided by the Sponsor prior to all other non-PRO assessments and before the patient receives any disease-status information during that assessment. ATAQ questionnaires should be administered to subjects enrolled in Part b of the study.
- ^r The End of Study Questionnaire should be administered to subjects enrolled in Part B of the study.

6. Study Treatments

The study drug is GBT440 300 mg capsules or placebo.

Subjects randomized to the following treatment groups in Part A will receive:

- GBT440 900 mg -- 3 GBT440 300 mg capsules
- GBT440 600 mg -- 2 GBT440 300 mg capsules and 1 placebo capsule.
- Placebo -- 3 placebo capsules.

Subjects randomized to the following treatment groups in Part B will receive:

- GBT440 1500 mg -- 5 GBT440 300 mg capsules
- GBT440 600 mg -- 2 GBT440 300 mg capsules and 3 placebo capsules.
- Placebo -- 5 placebo capsules.

Study drug is to be dosed orally once daily for a total of 28 days.

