9.1 Safety Population

All subjects who receive any amount of study drug will be included in the Safety population. Subjects will be analyzed based on study drug received. This is the primary population for all safety analyses performed for this study.

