10.3 Data Analysis Conventions

Analyses for SMC meetings, interim analyses, and final data analysis will be performed by Statistics & Data Corporation (SDC). The final data analyses will be performed after Part B of the study is completed and the database has been locked. Data from Parts A and B of the study will be pooled across the common treatment arms (GBT440 600 mg and placebo arms). Statistical programming and analyses will be performed using SAS® Version 9.4 or higher. All study data will be listed by subject, study drug,

and visit (as applicable) based on randomized and treated subjects unless otherwise specified. Summary statistics will be presented by treatment group including all GBT440, and will include a total column where appropriate.

Study visits will be referred to in all tables and listings as the visit name corresponding to the planned study visit.

Summaries for continuous and ordinal variables will include the number of observations (n), arithmetic mean, standard deviation (SD), median, minimum, and maximum). Minima and maxima will be reported with the same precision as the raw values; means and medians will be presented to one additional decimal place than reported in the raw values. Standard deviations will be presented to two additional decimal places than reported in the raw values. Summaries for discrete variables will include frequency counts and percentages. All percentages will be rounded to one decimal place (i.e., XX.X%).

All statistical tests will be two-sided with a significance level of 0.05 ($\alpha = 0.05$) unless otherwise specified. Confidence intervals (CI) for differences between treatment groups will be two-sided at 95% confidence. All p values will be rounded to four decimal places; p-values less than 0.0001 will be presented as “<0.0001”; p-values greater than 0.9999 will be presented as “>0.9999”.

All summary tables will be supported with subject listings.

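### The End of Study Questionnaire is given only in Part B, but SAP 17.9, read literally, takes percentages over a Safety population that includes Part A subjects who were never asked

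*SAP*

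**What the plan says.** SAP 17.9 describes an eight-item, self-administered survey at the Day 58 visit and limits who receives it: "The survey is to be completed by subjects enrolled under Part B of the trial". The footnote to the schedule in SAP 5.1 repeats the limit ("The End of Study Questionnaire should be administered to subjects enrolled in Part B of the study"), as do protocol section 5.5.5.6 and the footnotes to protocol Appendix A. The last sentence of SAP 17.9 gives the summary rule: "All responses will be summarized with the number and percentage of subjects in the Safety population by study drug and all GBT440".

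SAP 9.1 defines that population without reference to part: "All subjects who receive any amount of study drug will be included in the Safety population". SAP 10.3 sets the pooling convention for the final analysis: "Data from Parts A and B of the study will be pooled across the common treatment arms (GBT440 600 mg and placebo arms"). Protocol section 11 says the same. Nothing in SAP 17.9, or elsewhere in either document, limits the questionnaire percentages to Part B subjects or to those who answered.

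**The concern.** A percentage of respondents makes sense only if everyone in the denominator could have responded. Here the Part A subjects could not: they were never given the survey, and SAP 10.1.2 rules out imputation, so they can add only to the denominator. The dilution also differs by dose. Placebo and 600 mg mix the two parts, 900 mg exists only in Part A, and 1500 mg exists only in Part B, so 1500 mg alone is undiluted. The survey asks about symptoms and about changes in oxygen saturation and use. A table that shows a large difference between 1500 mg and placebo on such items, when there is none, could be misread.

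**Working it through.** **Inputs.** Part A allocation (SAP section 4): "randomized 1:1:1 to receive GBT440 900 mg (n = 6) or 600 mg (n = 6), or placebo (n = 6"). Part B allocation (same section): "randomized 3:1:1 to receive GBT440 1500 mg (n = 9) or 600 mg (n = 3), or placebo (n = 3"). Check against the stated total: 6 + 6 + 6 = 18 and 9 + 3 + 3 = 15, and 18 + 15 = 33, which matches the approximately 33 in SAP section 7. The documents state no figure for the questionnaire percentages themselves.

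**Formula.** For a column with a Part A subjects and b Part B subjects, the highest attainable percentage under the literal rule is b / (a + b).

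| Column | Part A (a) | Part B (b) | Safety population (a + b) | Highest attainable |
|---|---|---|---|---|
| Placebo | 6 | 3 | 9 | 3/9 = 33.3% |
| 600 mg | 6 | 3 | 9 | 3/9 = 33.3% |
| 900 mg | 6 | 0 | 6 | 0/6 = 0% |
| 1500 mg | 0 | 9 | 9 | 9/9 = 100% |
| All GBT440 | 12 | 12 | 24 | 12/24 = 50% |

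**What identical answers would look like.** Assume, for illustration, that two thirds of the Part B subjects in every arm choose the same option.

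| Column | Literal rule | Part B denominator |
|---|---|---|
| Placebo | 2/9 = 22.2% | 2/3 = 66.7% |
| 600 mg | 2/9 = 22.2% | 2/3 = 66.7% |
| 1500 mg | 6/9 = 66.7% | 6/9 = 66.7% |
| All GBT440 | 8/24 = 33.3% | 8/12 = 66.7% |

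The literal rule shows a gap of 66.7 − 22.2 = 44.4 points (6/9 − 2/9 = 4/9) between 1500 mg and placebo where there is none. In general, if a proportion p of every Part B arm gives an answer, the spurious gap is p − p/3 = 2p/3. This holds for any answer, favourable or not.

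**Sensitivity to arm size.** Planned sizes are given as approximately 18 and up to 15. Assume that a pooled arm ends with 5 to 7 Part A and 2 to 4 Part B subjects. The ceiling then runs from 2/(7 + 2) = 22.2% to 4/(5 + 4) = 44.4%, still far below 100%.

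**The case against.** The strongest reply is that SAP 17.9 names an analysis set and does not fix a denominator. Where this SAP wants to fix one, as for disposition in section 11, it says so outright. The sentence before the rule limits the survey to Part B, so a programmer might sensibly divide by respondents. This stands in part: the word is absent and the right table could still be produced. But the wording as it stands points to the Safety population, and no other section corrects it.

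A reader might infer that the rule favours 1500 mg. The documents do not support that. The eight items and their response options are not shown, and the rule scales every option down equally in the pooled arms. An answer such as worse symptoms or more oxygen use would also look more frequent on 1500 mg.

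A reader might also infer that the ATAQ oxygen-use percentages in SAP 17.6.3 share the fault. That sentence reads "Responses to questions regarding supplemental oxygen use will be summarized with the number and percentage of subjects in each treatment group", and does not name the Safety population. The section works in the Efficacy-Evaluable population, and SAP 17.6 opens by confining ATAQ to Part B. The denominators computed above do not apply there. At most the wording could be made explicit.

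Finally, the error would be partly visible: counts sit beside percentages, the 900 mg column would be all zeros, and SAP 10.3 requires subject listings behind every summary table. That helps an attentive reader, but 6/9 against 2/9 still misleads anyone who does not know that six of the nine placebo subjects were never asked.

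**Conclusion.** The concern holds for SAP 17.9. Applied literally, the rule caps responses at about 33% for placebo and 600 mg, 0% for 900 mg and 50% for All GBT440, against 100% for 1500 mg. Arms that answer identically would appear to differ. These figures rest on the planned allocation, on pooling under SAP 10.3, and on reading the Safety population as the denominator.

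The point is minor. A reader might take gaps of this size as a threat to the trial's conclusions, but the questionnaire is not among the primary, secondary or exploratory endpoints in either document. SAP 17.9 plans no model, interval or p-value, and the study has no formal hypotheses. The planned interim analyses cover primary and secondary endpoints in Part A, where the survey is not given, and the Safety Monitoring Committee reviews safety data. What is at stake is a correct descriptive table.

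**What to change.** In SAP 17.9, state that percentages are based on Part B Safety-population subjects who answered the item, and show that n in each column. Omit the 900 mg column, do not add Part A subjects to placebo or 600 mg, and define All GBT440 for this table as Part B 1500 mg plus 600 mg (9 + 3 = 12 as planned). Each remaining column can then reach 100%. With three planned subjects each on placebo and 600 mg, one answer moves the percentage by 33.3 points, so the counts should stay beside the percentages.

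As a consistency step only, state the same Part B denominator for the oxygen-use percentages in SAP 17.6.3, within the Efficacy-Evaluable population already named there.

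The cost is a sentence or two in the SAP and the matching denominators in the table programs. It needs no new data and no change to trial conduct.
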